4.3.2 Secondary Objectives

Secondary objectives include: (1) HIV risk behaviors (compared using repeated measures procedures to evaluate possible change in sexual and drug-related behaviors that may inhibit or promote HIV infection) measured by the HIV-GAIN; (2) Self-reported number of days incarcerated during the intervention and follow-up phases; (3) Self-reported number of days of opioid and other drug use measured by TLFB, and objective measures of drug use by urine drug screens (UDS) at the 6-month post-release assessment (end of the intervention phase); (4) Self-reported days in drug abuse treatment; (5) Self-reported number of arrests; (6) Self-reported craving for opioids, and (7) Self-reported number of overdoses.

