6.2 Secondary Outcome Measures

- HIV risk behaviors (compared using repeated measures procedures to evaluate possible change in sexual and drug-related behaviors that may inhibit or promote HIV infection) measured by the HIV-GAIN;
- (2) Self-reported number of days incarcerated during the intervention and follow-up phases;
- (3) Self-reported number of days of opioid and other drug use measured by TLFB, and objective measures of drug use by urine drug screens (UDS) at the 6-month post-release assessment (end of the intervention phase);
- (4) Self-reported days in drug abuse treatment;
- (5) Self-reported number of arrests;
- (6) Self-reported craving for opioids;
- (7) Self-reported number of overdoses; and
- (8) Self-reported motivation for treatment.

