7.3 Random Assignment

Eligible participants will be randomly assigned to study condition (VI, PNV, DE) in a 1:1:1 strategy using an urn randomization procedure (Stout et al., 1994) to provide multivariate balance across two characteristics correlated with outcomes in addiction treatment trials: type of opioid (heroin or prescription drug) and gender.

Individuals who terminate participation before induction onto the assigned medication (or similar time-point for behavioral assignments) will be replaced. Those terminating after VI induction or provision of the first DE session will not be replaced and will be counted as "treatment failures" (in an intent-to-treat scenario).

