10.0 STATISTICAL ANALYSES

The project emphasizes evaluation of the clinical utility of Vivitrol in jail inmates as compared with a Drug Education condition (DE), while descriptive statistics will provide an overall assessment of the implementation of the protocol.

Analyses will include an Intent-to-treat (ITT) design such that all randomized participants who received at least one dose of medication (VI, PNV), or received at least one session of drug education (DE) will be included who did not violate the protocol in a way that could potentially affect the efficacy results. Participants will be excluded from the Protocol Population (PP) if:

- 1. concomitant medication that is known to have significant clinical effect on primary or secondary endpoints was administered.
- 2. Violations of the inclusion or exclusion criteria are judged to affect the efficacy evaluations.

Subjects in the PP population will be allocated to treatment groups in the analysis based on the actual treatment they received. If there is substantial difference between the ITT population and the PP population, all analyses described below will be performed using only subjects in this group.

All statistical tests will be performed using two-sided .05 significance levels, unless otherwise stated. All comparisons between treatments will be reported with parameter estimates and 95% confidence intervals. For parameters measured at baseline and subsequently, the variables of interest are changes from baseline.

Post-baseline variables will not be imputed; estimates can be obtained using the hierarchical models specified below under the assumption of missing at random. For the primary outcome measure, diagnosis at six months, subjects who have dropped out for whatever reason will be considered to retain the diagnosis. Other outcome measures for which data are missing will be imputed using multiple imputation methods. Sensitivity analyses will repeat specific analyses using permutation tests of at least 1000 samples.

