10.2 Secondary Outcomes

Analyses will include descriptive, binomial and multinomial methods to address secondary outcomes:

- HIV risk behaviors (compared using repeated measures procedures to evaluate possible change in sexual and drug-related behaviors that may inhibit or promote HIV infection) measured by the HIV-GAIN;
- (2) Self-reported number of days incarcerated during the intervention and follow-up phases;
- (3) Self-reported number of days of opioid and other drug use measured by TLFB, and

objective measures of drug use by urine drug screens (UDS) at the 6-month post-release assessment (end of the intervention phase);

- (4) Self-reported days in drug abuse treatment;
- (5) Self-reported number of arrests;
- (6) Self-reported craving for opioids;
- (7) Self-reported number of overdoses; and
- (8) Self-reported motivation for treatment.

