10.4.1 Data Screening

Typical data screening activities will be conducted; univariate analyses will determine cell frequencies, normality, linearity, and homoscedasticity of continuous variables, and missing values. Variables with non-normal distributions will be transformed, when appropriate, using procedures recommended by Mosteller and Tukey (1977). Missing values will be handled using conventional case elimination, mean substitution, or estimation procedures (e.g. Cohen & Cohen, 1983). Preliminary analyses will address baseline characteristics of the two medication conditions using univariate techniques to determine the adequacy of the random assignment procedures, and whether these procedures result in groups similar in pertinent characteristics. Any variables determined to differ significantly between conditions will be used as covariates. We will also conduct attrition analyses to determine whether participants who failed post-consent screening differ from those randomized.

Baseline Characteristics and Treatment Group Differences

To appraise differences in baseline characteristics of the treatment groups, continuous variables will utilize analysis of variance, ordinal variables will utilize the Cochran Mantel Haenszel test, and dichotomous variables will utilize the chi-square (χ^2) test or Barnard's test. As appropriate, transformation such as log, square root or inverse may be utilized to accomplish the twin goals of variance stabilization across levels of the predictor variables and normal distribution of the outcome variable, if necessary.

For continuous variables, the number of non-missing and missing values and the median, mean, standard deviation, minimum, and maximum will be obtained for each treatment group. For categorical variables, the counts and proportions of each value will be tabulated.

Differences between participants who were considered but not randomized (screen fails) will be compared with randomized participants on selected demographic characteristics. Summary tables for continuous variables include mean, standard deviation, median, min and max will be prepared. Outcome measures will be summarized by treatment group and by visit when applicable.

Treatment group differences at the 0.10 level of significance in baseline variables may be included as stratification variables or covariates in efficacy analyses.

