10.4.2 Primary Statistical Analysis of the First Primary Outcome Measure

A mixed effects logistic regression will used to model the binary primary outcome measure; the diagnosis of opioid use disorder at six months post treatment. are modeled as a linear combination of predictor variables. A logit link function will be used to link subject covariates to the probability of success There will be two levels in the model: within sites and between sites. The model will included treatment, cluster (site) and baseline covariates as fixed effects and subject as a random effect. Indicator variables will identify whether a subject has received XR-NTX, methadone and a behavioral intervention (PN.) Site by treatment interactions will be included in the model. Interactions that are statistically significant at the 10% level will be investigated and may imply that analyses of individual sites is required. In this case, relevant contrasts will be performed within the sites.

Additional covariates will include age, gender, whether a subject had prior methadone maintenance treatment and baseline self-reported cocaine use. Other possibilities mediating

factors include opioid dependence severity at baseline, concurrent cocaine or alcohol and/or benzodiazepine misuse, and homelessness.

SAS PROC Mixed will be used to perform the analysis. The coefficients in the model will be estimated by generalized least squares (GLS), with covariance parameters estimated by restricted maximum likelihood (REML). Standard errors of the parameter estimates will be computed using the model. This procedure assumes that missing observations are ignorably missing or missing at random (MAR).

The primary contrast is a comparison of the probability of a DSM-5 Opioid Use Disorder Diagnosis at 6 months for those on medication versus those receiving enhanced treatment as usual (etau.) The contrast will utilize XR NTX data from both the NYU and UCLA and Interim Methadone data from FRI; the medication plus PN treatment arm will not be included.

Descriptive statistics will examine feasibility issues of the pharmacotherapy, analyzing AEs, side effects, and patient and clinician acceptance, and reasons for early termination or post-randomization refusal of assigned condition. Single-point, between-group comparisons of these measures can be tested using t-tests or ANOVAs for continuous variables and chi-square for binary measures.

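### Secondary outcome 7 counts only self-reported overdoses, so a fatal overdose cannot enter the trial's only named overdose outcome, although deaths are already reported as SAEs.

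*Combined protocol and SAP*

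**What the plan says.** Section 6.2 lists "Self-reported number of overdoses" as the seventh secondary outcome. Sections 4.3.2 and 10.2 repeat it with self-report as the only source. Table 1 in Section 8.0 has no separate overdose instrument.

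Several rules could apply to a participant who dies:

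- Section 10.0 first says "Post-baseline variables will not be imputed", then says "Other outcome measures for which data are missing will be imputed using multiple imputation methods".
- Section 10.4.1 says "Missing values will be handled using conventional case elimination, mean substitution, or estimation procedures".
- Section 7.3 says of those who stop after induction or the first education session that they "will not be replaced and will be counted as" treatment failures.

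On the safety side, Appendix A makes any death in the study or its follow-up period a reportable SAE, whether or not the intervention caused it. Section 11.22.3 puts all SAEs into the data system. Appendix A also allows autopsy and medical records to be obtained for a serious event. Section 10.4.2 plans descriptive work "analyzing AEs, side effects, and patient and clinician acceptance" and does not mention overdose.

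**The concern.** Section 4.1 identifies overdose as the main cause of death in the first two weeks after release, and the drug education arm is built partly around preventing it (Sections 2.2 and 2.4). An overdose outcome in this population should be able to register a death. As defined, it registers the less serious form of the event and omits the most serious one. An arm in which someone dies of an overdose would look slightly better on this outcome than an arm in which someone overdoses, survives and says so.

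At stake is the reading of one secondary comparison. Someone looking only at the overdose result would not see the fatal events and would have to find them in general adverse event listings.

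**Working it through.** The plan gives no figure for this outcome, so there is none to reproduce. The check has two parts.

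**1. Does any rule put a fatal overdose into the count?**

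- *Outcome definition (4.3.2, 6.2, 10.2):* self-report only, with no second source and no provision for death. By contrast, outcome 3 in Section 6.2 pairs self-reported use with urine screens.
- *Imputation (10.0):* one sentence rules it out for post-baseline variables and another prescribes multiple imputation. Neither assigns an event because of a death.
- *Data screening (10.4.1):* case elimination removes the participant, and mean substitution gives an average. Neither adds the event.
- *Treatment failure label (7.3):* it gives no value for a count.
- *Dropouts keep the diagnosis (10.0):* this covers only the six-month diagnosis.

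No rule counts the death as an overdose. Non-fatal overdoses reported before the death can still count; only the fatal event is lost by definition.

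**2. How large is one omission?**

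Inputs from Section 10.3: 50 participants per arm, and about 120 evaluable in total, so 120/3 = 40 per arm. The documents give no overdose rate. I therefore assume T overdoses in an arm (T = 1, 5 or 10), exactly one of them fatal, in a participant with no earlier reported overdose. The n = 50 rows assume everyone else in the arm is fully followed. The n = 40 rows treat the participant who died as one of the 40.

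- Fatal event counted: mean = T/n.
- Participant dropped, or given the survivors' mean: mean = (T − 1)/(n − 1). Shortfall = T/n − (T − 1)/(n − 1) = (n − T)/[n(n − 1)].
- Participant kept with pre-death reports only: mean = (T − 1)/n. Shortfall = 1/n.

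| n | T | Fatal event counted | Dropped or mean-substituted | Shortfall | Pre-death reports kept | Shortfall |
|---|---|---|---|---|---|---|
| 50 | 1 | 0.020 | 0.000 | 0.020 | 0.000 | 0.020 |
| 50 | 5 | 0.100 | 0.082 | 0.018 | 0.080 | 0.020 |
| 50 | 10 | 0.200 | 0.184 | 0.016 | 0.180 | 0.020 |
| 40 | 1 | 0.025 | 0.000 | 0.025 | 0.000 | 0.025 |
| 40 | 5 | 0.125 | 0.103 | 0.022 | 0.100 | 0.025 |
| 40 | 10 | 0.250 | 0.231 | 0.019 | 0.225 | 0.025 |

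Two limits apply. Under mean substitution the arm total is not exactly one too low: with n = 50 and T = 10 it becomes 9 × 50/49 = 9.18, a shortfall of 0.82. Multiple imputation, which Section 10.0 names, draws from a model and need not centre on the survivors' mean, so the table does not cover it. The usable summary is about 1/50 = 0.02 per randomized participant, or about 1/40 = 0.025 per evaluable participant, for each fatal overdose.

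**The case against.** The strongest reply is that fatal overdoses are already captured and reviewed. Every death is an SAE, SAEs go to the DSMB as they occur (Section 11.6), and adverse events are to be analyzed (Section 10.4.2). Reporting deaths as safety events and non-fatal overdoses as a self-report outcome is a defensible split. Death is not ignored in efficacy either: under the dropout rule in Section 10.0, a participant who dies plausibly counts as keeping the diagnosis on the DSM-5 primary outcome. Most of this stands and keeps the point minor. But the plan does not state the split as its intention, and the adverse event analysis does not name overdose, so the overdose comparison remains incomplete.

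A reader might infer three stronger claims that the documents do not support:

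- *That fatal overdoses are lost to the trial.* They are not, given the SAE rules. Those rules carry no arm restriction, and Section 2.2 has weekly adverse event calls to all participants.
- *That the omission biases the comparison between arms.* Section 2.4 mentions naloxone kits for the education arm, which could turn deaths into survived overdoses there. That is a possible mechanism only; no document gives fatal or non-fatal overdose rates by arm.
- *That deaths are missed because adverse event windows differ.* Section 11.22.1 stops at the post-medication assessment, while Appendix A runs to 30 days after the last visit. But the death clause in Appendix A separately reaches the follow-up period, so this adds little.

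The conflict among the imputation statements is also real, but it is a general defect affecting many outcomes.

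**Conclusion.** The point holds as a gap in an outcome definition. Followed as written, the plan excludes fatal overdose from its only named overdose outcome, although the deaths are already collected. Each fatal overdose is one event omitted from its arm, on the scale worked out above, with the exact shortfall set by the missing-data method. How many such deaths will occur cannot be estimated from the documents; with none, the effect is zero.

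The wording gap is certain. The size rests on the arm sizes in Section 10.3 and on my assumed overdose counts. The primary outcomes, the sample size and the safety protections are unaffected. This is one of eight secondary outcomes in a trial that Section 10.3 describes as preliminary, so I rate it a minor, inexpensive improvement.

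**What to change.** Amend Sections 4.3.2, 6.2 and 10.2 as follows:

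- Define outcome 7 as any overdose, fatal or non-fatal, from self-report plus the SAE and death reports already collected.
- State one window for all arms, for example randomization to month 12, the last assessment at which Table 1 schedules adverse event collection.
- Count a death attributed to overdose as an event; do not drop or impute it.
- Show fatal and non-fatal counts separately by randomized arm.
- Add a short cause-of-death rule naming the records used. Apply it blind to arm, because the trial is open-label (Section 7.14) and attribution involves judgement. List deaths of unknown cause separately.

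The cost is mainly wording; no visit or instrument is added. Self-report and SAE records must be merged and de-duplicated, and records that Appendix A treats as optional may need to be requested more often. The two sources will not be equally complete, since some deaths are known only if they come to staff attention, and some will stay unattributed. Separate fatal and non-fatal counts keep that visible.

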7.0 STUDY PROCEDURES

7.1 The Consent Process

This study will be reviewed and approved by the Medical Institutional Review Board (M-IRB) of the University of California, Los Angeles, and the Institutional Review Board of the University of New Mexico.

All participants will voluntarily sign an informed consent prior to study participation. The informed consent process involves a detailed verbal description of the study and the data collection procedures. The participant will be encouraged to ask questions about the study procedures throughout the process. The risks of participating in this study will be detailed in the consent form. Staff will emphasize that participation is voluntary and that participants may withdraw consent at any time without prejudice, and will be given referrals to other local treatment programs.

After discussing the study procedures, potential risks and benefits, the voluntary nature of study participation, and that participation will have no effect on a participant's sentence, jail term, probation, parole, or release, study candidates will answer a brief quiz to verify and document a thorough understanding of the research prior to signing the consent form. The study candidate will sign the consent form as witnessed by a study investigator or physician. Research staff will receive extensive training in the informed consent process. A copy of the signed consent form will be given to all participants

7.2 Screening

The study team will provide a basic description of the study to interested individuals who respond to IRB-approved flyers and announcements at BCMDC. Study staff will verify pre-eligibility status of each study candidate with jail staff (e.g., has completed opioid detoxification, jail term and expected release date). Individuals determined as pre-eligible will be scheduled for a consent/screening appointment. Screening will begin with the informed consent process. A complete medical history and physical exam will occur after consent. Participants will be randomized to study condition when results of all assessments, including blood chemistries and ECG, are obtained and eligibility is confirmed. Screening will take ~4 hours, excluding review of lab results. This process may occur over multiple days.

7.3 Random Assignment

Eligible participants will be randomly assigned to study condition (VI, PNV, DE) in a 1:1:1 strategy using an urn randomization procedure (Stout et al., 1994) to provide multivariate balance across two characteristics correlated with outcomes in addiction treatment trials: type of opioid (heroin or prescription drug) and gender.

Individuals who terminate participation before induction onto the assigned medication (or similar time-point for behavioral assignments) will be replaced. Those terminating after VI induction or provision of the first DE session will not be replaced and will be counted as "treatment failures" (in an intent-to-treat scenario).

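### Type of opioid balances the randomisation but is not named as a covariate in the primary model: a small loss that is nearly free to remove

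*Combined protocol and SAP*

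**What the plan says.** Section 7.3 sets the allocation: "Eligible participants will be randomly assigned to study condition (VI, PNV, DE) in a 1:1:1 strategy using an urn randomization procedure". The balancing factors are "two characteristics correlated with outcomes in addiction treatment trials: type of opioid (heroin or prescription drug) and gender".

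Section 10.4.2 gives the primary model, a mixed effects logistic regression for the six-month diagnosis. On its terms: "The model will included treatment, cluster (site) and baseline covariates as fixed effects and subject as a random effect". It then says: "Additional covariates will include age, gender, whether a subject had prior methadone maintenance treatment and baseline self-reported cocaine use". A further list of possible factors reads: "factors include opioid dependence severity at baseline, concurrent cocaine or alcohol and/or benzodiazepine misuse, and homelessness". Type of opioid is in neither list and is named nowhere else in section 10.

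Section 10.4.1 has two rules that admit covariates after looking at the data. One is optional: "Treatment group differences at the 0.10 level of significance in baseline variables may be included as stratification variables or covariates in efficacy analyses". The other is firm: "Any variables determined to differ significantly between conditions will be used as covariates". It follows a sentence about comparing the two medication conditions, so it is not clear that it covers the DE arm.

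Two other places matter. Section 10.0 plans permutation tests as sensitivity analyses without saying whether they follow the urn. Section 10.4.2 covers only the first primary outcome. No model or covariate set is given for the other, days of opioid use in the past 30 days (section 2.4, Analyses).

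**The concern.** The usual practice is to analyse by the factors used to balance allocation. Here the trial chose two factors because it regards both as related to outcome, then carried only one by name into the primary model. The text gives no reason for treating them differently.

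At stake are some efficiency, the size of the reported odds ratio, and pre-specification. If type of opioid enters only through a baseline test, the form of the primary model depends on the data, although the reason for including the factor was known at the design stage.

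**Working it through.** **Step 1: compare design and model.**

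| Factor | Urn (7.3) | Named covariate (10.4.2) | Listed as possible factor (10.4.2) |
|---|---|---|---|
| Gender | yes | yes | – |
| Type of opioid | yes | no | no |

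**Step 2: look for another way in.** The term for baseline covariates in the fixed-effects sentence is undefined, so it does not pre-specify type of opioid. The section 10.4.1 rules need an observed difference between groups. Under simple randomisation a test at the 0.10 level would fire by chance about 10% of the time, and one at 0.05 about 5%. The urn is meant to make imbalance on this factor rarer still. Inclusion is therefore possible but unlikely.

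**Step 3: size for the diagnosis outcome.** The plan gives no figure on this point to reproduce. It also gives no opioid-type mix, prognostic strength or diagnosis rates, so these are assumptions: 60% or 80% in one opioid class, opioid-type odds ratio 1.5, 2.5 or 4, control diagnosis rate 60%, treatment odds ratio 1 or 0.33. From the documents: 50 per arm (section 10.3) and the error rate (section 10.0: "All statistical tests will be performed using two-sided .05 significance levels, unless otherwise stated"). Logistic regressions were fitted to 4,000 simulated two-arm data sets per scenario, with opioid type exactly balanced. Each data set was analysed without and with the factor.

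| Class mix | Opioid-type OR | Type I error, without / with | Power, without / with | Median treatment log OR, without / with |
|---|---|---|---|---|
| 80% | 1.5 | 0.051 / 0.052 | 0.792 / 0.792 | −1.151 / −1.154 |
| 80% | 2.5 | 0.049 / 0.051 | 0.764 / 0.764 | −1.071 / −1.127 |
| 80% | 4 | 0.043 / 0.047 | 0.759 / 0.761 | −1.069 / −1.138 |
| 60% | 1.5 | 0.052 / 0.053 | 0.804 / 0.804 | −1.151 / −1.156 |
| 60% | 2.5 | 0.056 / 0.060 | 0.766 / 0.767 | −1.069 / −1.132 |
| 60% | 4 | 0.042 / 0.052 | 0.722 / 0.733 | −0.995 / −1.147 |

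- Simulation error of a type I rate: √(0.05 × 0.95 / 4000) = 0.0034. The 0.060 stands out, but a repeat with another seed did not reproduce it. The gap at 60% and OR 4 did recur.
- Largest power difference: 0.733 − 0.722 = 0.011, about one point.
- Largest shift in the estimate: exp(−0.995) = 0.37 without the factor, exp(−1.147) = 0.32 with it.
- In that same scenario the standard error of the treatment log odds ratio is about 0.42 without the factor and 0.45 with it. Adjustment moves the estimate away from zero and widens the interval on the log-odds scale.

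**Step 4: size for days of opioid use.** For a linear model, if type of opioid explains a share R² of the variance, leaving it out costs about R² × n participants. Assume R² of 5% to 10%. A VI v DE comparison uses about two thirds of the 120 evaluable, 120 × 2/3 = 80. The cost is then 0.05 × 80 = 4 to 0.10 × 80 = 8 participants. Adjusted intervals would be √0.95 = 0.975 to √0.90 = 0.949 times as wide, so 2.5% to 5% narrower.

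**The case against.** The strongest reply is that the practical effect is close to nil, and for the outcome with a specified model that is largely right. A reader might infer that the primary confidence interval is too wide because variance from opioid type is left in the error term. That is linear-model reasoning. The only specified primary model is logistic, and Step 3 shows the reverse on the log-odds scale. A reader might also carry a figure such as 6 to 12 of the 120 participants (5% to 10% of 120) to the primary analysis. That does not hold either: it applies only to a continuous outcome, which has no specified model, and 120 is not the base of the primary contrast, which excludes the medication-plus-navigator arm. Nor does the omission invalidate the test when the arms are balanced.

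It is also fair to say that the plan does not exclude type of opioid. The covariate list is introduced as additional to undefined baseline covariates, so the accurate description is that the factor is not named. The design already uses it through the urn.

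Finally, the primary contrast combines extended-release naltrexone data from two sites with interim methadone data from a third. The documents do not say whether the other sites recorded or balanced on opioid type. If they did not, the covariate would be missing for whole sites. That objection stands and limits the fix.

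What remains is that none of this pre-specifies a factor the trial itself calls prognostic, and the section 10.4.1 rules would rarely admit one that the urn has balanced.

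**Conclusion.** The mismatch between sections 7.3 and 10.4.2 is clear from the text. Its effect is small: at most about one point of power, slight conservatism (type I error 0.042 against 0.052) in the strongest scenario, and a treatment odds ratio nearer 1. Part of that last shift reflects a change of quantity, since odds ratios with and without a prognostic covariate differ even when the arms are balanced. For opioid-use days a modest loss of precision is possible.

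These sizes rest on the assumed mix, opioid-type odds ratios, diagnosis rates and R². They also rest on exact balance, and on two arms of 50 without site or the other covariates. Any overlap between type of opioid and covariates already named, such as prior methadone treatment, would reduce the gain. This is a low-severity point, worth acting on because the correction costs so little.

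**What to change.** 1. In section 10.4.2, name type of opioid (heroin v prescription) with gender as a pre-specified fixed covariate for the diagnosis outcome, regardless of observed balance.
2. State that the same covariates apply to days of opioid use.
3. In section 10.0, say that any permutation test respects both urn factors.
4. For the pooled primary contrast, state whether the other sites recorded type of opioid. Use it there only if they did; otherwise adjust for it in the analysis of this trial's own data.

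The cost is a few sentences, made before the data are analysed. No sample size or error rate changes. For this trial the variable must be known at randomisation because the urn uses it; the only outside check is what the other sites hold.
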